4. PART 2 – DOUBLE-BLIND PLACEBO-CONTROLLED

4.1. Part 2 Objectives and Endpoints

Objectives	Endpoints		
Primary			
To assess the efficacy of prophylactic VXA-CoV2-1.1-S against confirmed COVID-19 occurring from 7 days after second dose with a repeat-dose vaccination schedule in healthy adults compared to placebo	• Frequency duration and severity of virologically confirmed COVID-19 illness and serologically confirmed SARS-CoV-2 infection occurring from 7 days following second study drug dose administration		
To evaluate the safety and tolerability of VXA-CoV2-1.1-S with a repeat-dose vaccination schedule in healthy adults compared to placebo	 Frequency, duration, and severity of solicited symptoms of reactogenicity (local, systemic) for 1 week following each vaccination Frequency, duration, and severity of unsolicited TEAEs, SAEs, and MAAEs through the active period (4 weeks post last dose), efficacy period and safety follow-up period. MAAEs will be determined by (1) active monitoring for COVID-19 and VAED through the active period (4 weeks post last dose), and (2) monitoring for potential immune-mediated medical conditions including AESIs and NOCIs for one year post last dose. 		
Secondary			
To assess long-term safety of VXA-CoV2-1.1-S	• Frequency, duration, and severity of all SAEs, and MAAEs including monitoring for COVID-19 and potential VAED, AESIs and NOCIs through one year post last dose.		
To assess the immunogenicity of VXA-CoV2-1.1-S with a repeat- dose vaccination schedule in healthy adults compared to placebo	 Key immunogenicity endpoints: SARS-CoV2-specific IgG and IgA antibody levels using MSD assays Neutralizing serum antibody titers to SARS-CoV-2 Additional immunogenicity endpoints: Antigen S-specific IgA in nasal swabs Antigen S-specific IgA in saliva 		

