5.4.3. Blinding and Unblinding (Part 2 only)

Participants, Investigators, site personnel and the Sponsor (except as described below) will be blinded to individual participant treatment assignment in Part 2.

Study drug doses will be prepared at the study sites by an unblinded research pharmacist(s) who will be provided treatment assignment through a RTSM System.

Sponsor representative(s) will also have access to unblinded individual participant treatment assignments for the purposes of study-required activities, including management of study drug inventory, production of summaries of data for IDMC review, and performance of bioanalytical analysis. These personnel will not be directly involved in the conduct of the study.

An IDMC will periodically convene to review unblinded overall safety and emerging efficacy results (Section 8.5).

The RTSM system will be programmed with blind-breaking instructions. In case of a medical emergency, the Investigator has the sole responsibility for determining if unblinding of a participant's treatment assignment is warranted. Participant safety must always be the first consideration in making such a determination. The Investigator should notify the Sponsor's Medical Monitor (or designee) prior to unblinding using the RTSM system. The Investigator(s) must document and report to the Medical Monitor any breaking of the treatment code. The date and reason that the blind was broken must be recorded in the source documentation.

Appropriate personnel at the Sponsor (or designee) will unblind suspected unexpected serious adverse reactions (SUSARs) for the purpose of reporting to authorities as required per each local

regulation. The Sponsor will submit SUSARs to Regulatory Agencies in blinded or unblinded fashion according to local law. The Sponsor will submit SUSARs to Investigators in a blinded fashion.

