7.1.2. Immunogenicity

Samples will be collected from all participants for immunogenicity assessment according to the time points specified in the SoA (Section 1.2; Table 3 and Table 4). The following immunoassays will be performed:

Key immunogenicity assessments:

Part 1:

- SARS-CoV2-specific IgG/IgA by MSD (Serum)
- Neutralizing antibody titers to SARS-CoV-2 (Serum)

Part 2:

- SARS-CoV2-specific IgG/IgA by MSD (Serum)
- Neutralizing antibody titers to SARS-CoV-2 (Serum)

Additional Immunogenicity Assessments:

Part 1:

- T cell responses by intracellular cytokine cytometry (ICC)
- Antigen S-specific IgA (Nasal Swabs)

- Antigen S-specific IgA (Saliva)
- Anti Ad5 antibodies (optional), (Serum)

Part 2:

- Antigen S-specific IgA (Nasal Swabs)
- Antigen S-specific IgA (Saliva)

Additional exploratory immunoassays may also be run to further characterize the immune response of the VXA-CoV2-1.1-S vaccine. Sample collection, processing and shipping details are provided within the General and Immunogenicity Laboratory Manuals.

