Interim looks at the efficacy using O'Brien Fleming Boundaries. One interim analysis may be conducted during the study by the IDMC if 18 confirmed cases of COVID-19 are observed prior to the completion of Month 7 visits, 6 months following the second vaccination, by all subjects. Given a power estimate of 95%, the study may be stopped by the Sponsor for overwhelming efficacy at the interim look if alpha ≤ 0.003 . The study will continue if this criterion is not met (and may be continued even if it is met per Sponsor's review and FDA agreement). If the decision is made to continue the study until completion at 6 months post last vaccination, alpha ≤ 0.05 .

Analysis Population	Description
Screened	All subjects who enter screening (assigned a screening number)
Randomized	All participants who are assigned a randomization number
Dose 1 evaluable immunogenicity	All eligible randomized participants who receive the study intervention to which they are randomly assigned at the first dose, have at least 1 valid and determinate immunogenicity result after Dose 1, have blood collection within an appropriate window after Dose 1, and have no other important protocol deviations.
Dose 2 evaluable immunogenicity	All eligible randomized participants who receive 2 doses of the study intervention to which they are randomly assigned, within the predefined window, have at least 1 valid and determinate immunogenicity result after Dose 2, have blood collection within an appropriate window after Dose 2, and have no other important protocol deviations.
Dose 1 all-available immunogenicity	All randomized participants who receive at least 1 dose of the study intervention with at least 1 valid and determinate immunogenicity result after Dose 2.
Evaluable efficacy	All eligible randomized participants who receive all study intervention dose(s) as randomized within the predefined window and have no other important protocol deviations.
All-available efficacy	All randomized participants who receive at least 1 dose of the study intervention.
Safety	All randomized participants who receive at least 1 dose of the study drug.

8.2. **Populations for Analyses**

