	• Frequency, duration, and severity of unsolicited TEAEs, SAEs, and MAAEs through the active period (4 weeks post last dose) efficacy period and safety follow-up period. MAAEs include (1) active monitoring for COVID-19 and VAED through the active period (4 weeks post last dose); and (2) monitoring for potential immune-mediated medical conditions including AESIs and NOCIs for one year post last dose.
Secondary: Long-term Safety	Frequency, duration, and severity of all SAEs, and MAAEs including monitoring for COVID-19, AESIs and NOCIs through one year post last dose
	See section $\underline{8.2}$ (Populations for Analyses) for a descriptive of the populations used for these analyses.
Immunogenicity	Key immunogenicity endpoints:
	• SARS-CoV2-specific IgG and IgA antibody levels using MSD assays
	 Neutralizing serum antibody titers to SARS-CoV-2
	Additional immunogenicity endpoints:
	Antigen S-specific IgA in nasal swabs
	Antigen S-specific IgA in saliva
	Geometric mean titers/concentrations (GMTs/GMCs) of SARS-CoV-2 neutralizing titers, S-binding IgG level, and S- binding IgA level for SARS-CoV- 2 neutralizing titers, S-binding IgG levels, and S-binding IgA levels, GMTs/GMCs and 2-sided 95% CIs will be provided for by treatment group at the following time points:
	• Day 1, Week 4, Week 8, Month 7, and Month 13 after Dose 1
	Geometric means will be calculated as the mean of the assay results after making the logarithm transformation and then exponentiating the mean to express results on the original scale. Two-sided 95% CIs will be obtained by taking natural log transforms of concentrations/titers, calculating the 95% CI with reference to the t-distribution, and then exponentiating the confidence limits.
	GMFRs of SARS-CoV-2 neutralizing titers, S1-binding IgG level, and RBD-binding IgG level. For SARS-CoV-2 neutralizing titers, S1-binding IgG levels, and RBD-binding IgG levels, the GMFRs and 2-sided 95% CIs will be provided by treatment group at the following time points:
	• Day 1, Week 4, Week 8, Month 7, and Month 13 after Dose 1
	GMFRs will be limited to participants with non-missing values prior to the first dose and at the postvaccination time point. The GMFR will be calculated as the mean of the difference of logarithmically transformed assay results (later time point – earlier time point) and exponentiating the mean. The associated 2-sided

Vaxart,	Inc.
---------	------

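### Section 5.4.3 lets sponsor representatives hold Part 2 treatment assignments for bioanalytical work, so the key immunogenicity endpoints may be measured unblinded although the assays do not need the arm

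*Combined protocol and SAP*

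**What the plan says.** Section 5.4.3 applies to Part 2 only. Its general rule is: "Participants, Investigators, site personnel and the Sponsor (except as described below) will be blinded to individual participant treatment assignment in Part 2". The exception follows: "Sponsor representative(s) will also have access to unblinded individual participant treatment assignments for the purposes of study-required activities". Three activities are listed: "management of study drug inventory, production of summaries of data for IDMC review, and performance of bioanalytical analysis". One limit is placed on the people concerned: "These personnel will not be directly involved in the conduct of the study".

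The second Part 2 secondary objective in Section 4.1 is: "To assess the immunogenicity of VXA-CoV2-1.1-S with a repeat- dose vaccination schedule in healthy adults compared to placebo". Section 8.3.2 names two key endpoints for it. One is "SARS-CoV2-specific IgG and IgA antibody levels using MSD assays" and the other is the serum neutralizing titer. Nasal and saliva IgA are additional endpoints. Section 7.1.2 has samples taken from all participants at the scheduled visits, and Table 4 shows one schedule for both arms.

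Section 7.1.2 refers to a general and an immunogenicity laboratory manual, which it describes as covering sample collection, processing and shipping. Neither manual is part of the documents.

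**The concern.** The clause is a positive permission, not a missing detail. It lets people engaged in bioanalytical work see which participants received vaccine. Immunoassay results involve judgement: whether a run passes, whether an odd value is repeated, and which of two values is reported. If that judgement is made with the arm known, the GMTs, GMFRs and 4-fold response rates of Section 8.3.2 can drift apart between arms for reasons other than the vaccine.

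Two features raise the stakes. Section 8.4 brings immunogenicity through Week 8 into the interim analysis, while the trial is otherwise blinded. Section 8.1.2 gives the purpose of Part 2 as producing immunogenicity and efficacy results to guide later-stage studies. Values already read and accepted with the arm known cannot be made blind afterwards.

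**Working it through.** The plan states no figure on this point. The check is mainly a reading of sections side by side.

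1. **What bioanalytical analysis covers.** The term is not defined. No pharmacokinetic assay is planned. Apart from safety and infection testing, the Part 2 assays on participant samples are those in Section 7.1.2: serum IgG/IgA by MSD, neutralizing titers, nasal and saliva IgA, and possible exploratory immunoassays. The immunoassays are the natural reading, and both key endpoints are among them.
2. **Whether running the assay needs the arm.** In Table 4 the serum, nasal and saliva samples are taken at Day 1, Week 4, Week 8, Month 7 and Month 13, with no difference by arm. Section 8.3.2 uses the arm only when results are summarized by randomized group. IDMC summaries, which do need the arm, are a separate item in the same list in 5.4.3. Removing the bioanalytical item therefore disables nothing for the scheduled assays.
3. **Whether the safeguard reaches the risk.** Keeping these people out of study conduct separates them from sites and participants. It does not separate arm information from assay reading, repeats or acceptance. Nothing in the documents requires arm-blind assay runs, or final results before assignments are merged.
4. **When it applies.** Sections 4.2.2 and 5.9 unblind Part 2 after the last participant's Month 7 visit and database lock. Month 13 samples generally come later, so the exposure is mainly Day 1 to Month 7.

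**Illustration of size (all variances assumed).**
- Let the true log2 rise be N(μ, 1) and the assay SD be 0.5 log2 per result.
- The error of a rise then has variance 0.5² + 0.5² = 0.5, and the observed rise Z has variance 1 + 0.5 = 1.5.
- The 4-fold cut is log2 4 = 2, so the response rate is 1 − Φ((2 − μ)/√1.5).
- Suppose every vaccine-arm result with an observed 2- to 4-fold rise is repeated once and counted if the repeat passes, and no placebo result is repeated.
- The rate then grows by P(1 ≤ Z₁ < 2, Z₂ ≥ 2), with Z₁ and Z₂ bivariate normal. Their covariance is 1 if both samples are re-assayed. It is 1 + 0.25 = 1.25 if only the post-dose sample is.

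| Mean rise | No repeat | Both samples repeated | Post-dose sample only |
|---|---|---|---|
| 1-fold (μ = 0) | 5.1% | 7.1% | 7.1% |
| 2-fold (μ = 1) | 20.7% | 27.5% | 26.5% |
| 2.8-fold (μ = 1.5) | 34.2% | 43.5% | 41.9% |

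The gain is about 2 to 9 percentage points with both samples repeated, and about 2 to 8 with the post-dose sample only. The rule repeats roughly 16% to 32% of the vaccine arm.

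**The case against.** The strongest reply is that 5.4.3 grants access to sponsor representatives and does not say who runs, reads or accepts the assays. The work may be done by an external laboratory that is blinded under manuals not included here. The clause may have been meant only for selecting samples or merging results. This stands as far as it goes. A reader might infer that the endpoints are in fact measured unblinded, and the documents do not establish that. They permit it and state no safeguard against it. If the laboratory is blinded in practice, the protocol misdescribes that practice and still needs correcting.

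Other stronger readings also go beyond the text:

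- **That laboratory decisions settle who enters the evaluable sets.** The Dose 2 definition in Section 8.2 asks that participants "have at least 1 valid and determinate immunogenicity result after Dose 2". With several assays and visits, one rejected result would rarely remove anyone. Eligibility, dosing, blood-draw windows and protocol deviations also decide entry.
- **That no assay could ever use the arm.** Section 7.1.2 and Table 4 allow optional exploratory assays, and a stored baseline aliquot for testing after a clotting event. Arm-based selection is conceivable there, though not stated.
- **That primary efficacy is compromised.** Section 7.1.1 confirms COVID-19 by PCR or rapid molecular test, and site personnel are blinded. The primary endpoint also names serologically confirmed infection, but the documents do not say whether that test counts as bioanalytical.

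The scope is also limited. Immunogenicity is secondary in Part 2 and is summarized by group with confidence intervals, with no between-arm test specified.

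**Conclusion.** The concern holds as a permission that should not be there. Section 5.4.3 allows arm-aware work on the key secondary immunogenicity endpoints, gives no reason the scheduled assays would need it, and offers a safeguard that does not address it. The conclusion rests on one inference, that bioanalytical analysis means the immunoassays. The protocol offers no other natural candidate.

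The likely bias cannot be sized from the documents. The 2 to 9 point figure is close to an upper illustration. It assumes the variances and a deliberate-looking rule that repeats near-misses in one arm and counts only favourable repeats. It shows that the mechanism can matter and does not estimate what would happen. The change is worth making because the risk is avoidable at almost no cost and cannot be repaired once results have been accepted with the arm known.

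**What to change.** - **Section 5.4.3.** Delete bioanalytical analysis from the purposes for unblinded access. Keep drug inventory and IDMC summaries.
- **Add a statement on blinding.** The Part 2 immunogenicity assays are run, repeated and accepted or rejected by staff blinded to arm, on coded samples.
- **Add a statement on merging.** Assignments are joined to assay results only once the results are final. The unblinded statistics group does this for IDMC or interim summaries, and otherwise it happens after unblinding.
- **Optional or event-triggered assays.** If one needs samples chosen by arm, an unblinded person who does not read that assay makes the selection.

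The cost is a few sentences in the protocol and a matching line in the laboratory manual. No extra samples or assays are needed, and the scheduled immunogenicity and interim analyses are unaffected.

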5.5. Treatment of Overdose

Any overdose of study drug should be recorded in the eCRF (including quantity of the excess dose and the duration of the overdose). AEs associated with an overdose or incorrect administration of study drug should be recorded in the AE eCRF. An overdose will not be considered an SAE unless the outcome of the overdose meets seriousness criteria.

There is no specific management of an overdose of VXA-CoV2-1.1-S. Participants should be closely monitored for toxicities and managed appropriately.

5.6. Concomitant Therapy

Concomitant medication is defined as any prescription or over-the-counter preparation.

Use of concomitant medication from 4 weeks before Day 1 (Part 1 or Part 2) through 4 weeks after the last dose of study (completion of Active Period) must be recorded in the eCRF from the participant's medical file along with:

- Reason for use
- Dates of administration including start and end dates
- Dosage information including dose and frequency

Medications for pre-existing medical conditions or required for a medical condition during the study are allowed if not considered exclusionary.

The Sponsor's Medical Monitor (or designee) should be contacted if there are any questions regarding concomitant or prior therapy.

5.6.1. Prohibited Concomitant Medication

Medications specifically prohibited in the exclusion criteria are not allowed during the Active Period (Section 3.3.2 prior/concurrent therapy), unless deemed medically necessary by the Investigator.

5.7. Screen Failures

Screen failures are defined as participants who consent to participate in the clinical study but are not subsequently entered in the study. A minimal set of screen failure information is required to ensure transparent reporting of screen failure candidates to meet the Consolidated Standards of Reporting Trials (CONSORT) publishing requirements and to respond to queries from regulatory authorities. Minimal information includes demography, screen failure details, eligibility criteria, and any SAE.

Re-screening/re-assessment outside the Screening period will be possible on a case-by-case basis following Sponsor approval. Participants allowed to be re-screened will be assigned a new screening number (with referral in eCRF to the previous screening number); such participants will be determined a permanent screen failure after the second screening determines the participant is ineligible.

5.8. End of Study Definition

In both Part 1 and Part 2, a participant is considered to have completed the study if they complete the EOT visit at Week 8 (end of Active period). Participants are considered to complete Safety Follow-up if they complete the EOS visit at Month 13.

The end of the study is defined as the date of the last visit of the last participant in the study.

5.9. Intervention after the End of the Study

Following completion of the study Efficacy period in Part 2, the study database will be cleaned and locked and the treatment assignments unblinded. At this time subjects who were randomized to the placebo group under the current protocol will have the opportunity to receive vaccination(s) against COVID-19 via one of the following options:

- Receipt of an approved COVID-19 vaccine (standard-of care) in the region within which they are located (paid for by the Sponsor), or
- Receipt of a Vaxart oral tableted vaccine for the prevention of COVID-19 under an openlabel extension protocol

The specific approach to be utilized will be further defined and added to the protocol based on the availability of approved COVID-19 vaccines closer to the completion of Part 2.

6. DISCONTINUATION OF STUDY DRUG AND SUBJECT WITHDRAWAL FROM STUDY

6.1. Study Halting Rules

The study will be halted (no new enrollments and no further study vaccinations) pending an IDMC safety review if any of the below rules are met prior to the start of randomization in Part 2, or the end of the Active Period (4 weeks after the last study drug) in Part 1, whichever is later.

